Little is known about the best ways of communicating information about the benefits and harms of breast cancer screening mammography to racially/ethnically diverse women with varying levels of SES and health literacy. There is an urgent need for formative research to better understand these issues. Findings will inform strategies to support clinicians in communicating and individualizing discussion of the benefits and harms of screening, and will ultimately help enhance women's ability to make informed decisions about screening mammography. This is critical, as informed decision making takes into account empirical evidence and individuals' values and preferences, and is associated with better knowledge about screening guidelines and the benefits,

risks, and limitations of screening, less decisional conflict and anxiety, greater satisfaction with the decision making process or the decision, and active participation in the decision making process. 35,36

The goal of this project is to create decision support tools for Latina, Black, and non-Latina White women under age 50 with varying levels of health literacy who are considering breast cancer screening mammography.

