5.2.4 Data Scrubbing

After data collection, records will be removed from the final data set if they meet any of the following criteria as determined by members of the research team. Members of the research team will keep track of how many records were removed and for what reason(s).

Criteria for removal from the final data set:

- The participants do not meet all of the inclusion criteria; or
- The time to complete the questionnaire is less than half of the median time to complete the questionnaire across the full data set; or
- Participants do not respond to, provide nonsensical or incomprehensible answers to, or give responses in a language other than English to at least

four of the eight following knowledge questions:

- o 2.12 Tell me in your own words, what is a mammogram?
- 2.24. What is meant by the term "overdetection" (also called "overdiagnosis")? Please answer in English. If you are not sure, just guess.
- o 2.26. What are some of the benefits of breast cancer screening mammograms? Please answer in English.
- o 2.27. What are the risks or downsides of breast cancer screening mammograms? Please answer in English.
- o 3.49. Tell me in your own words, what is a breast cancer screening mammogram? Please answer in English
- 3.61. What is meant by the term "overdetection" (also called "overdiagnosis")? Please answer in English. If you are not sure, just guess.
- o 3.63. What are some of the benefits of breast cancer screening mammograms? Please answer in English.
- o 3.64. What are the risks or downsides of breast cancer screening mammograms? Please answer in English.

If a participant completes the questionnaire in less than half the median time, it is reasonable to believe that they were unable to process the decision aid(s) in sufficient detail to provide accurate responses to the questions.

Failing to adequately complete the knowledge questions (4 of which are pretool/control and 4 post-tool/control) limit the research team's ability to accurately analyze the feasibility, acceptability, usability, and limited-efficacy of the tool/control.

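### Section 5.2.4 removes a randomized woman's whole record for leaving four of eight knowledge questions blank, so selection into the analysis depends on the knowledge outcome and can bias the means and, in either direction, the difference

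*Combined protocol and SAP*

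**What the plan says.** Section 5.2.4 (Data Scrubbing), which applies once the data are in, states that "records will be removed from the final data set if they meet any of the following criteria as determined by members of the research team". One criterion covers records where "Participants do not respond to, provide nonsensical or incomprehensible answers to, or give responses in a language other than English to at least" a stated number of items; the threshold is given as "four of the eight following knowledge questions". The items are open-text: what a mammogram is, what overdetection means, the benefits and the downsides, each asked before and again after the material. The stated reason is that "Failing to adequately complete the knowledge questions (4 of which are pretool/control and 4 post-tool/control) limit" the team's ability to analyze feasibility, acceptability, usability and limited efficacy. The number of removals and the reasons are tracked; trial arm is not mentioned. Both overdetection items carry the prompt "If you are not sure, just guess"; the other six do not.

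Section 6.0 bases 33 women per arm in each racial/ethnic group partly on knowledge: control mean 57 of 100, difference 13, SD 20, one-sided Mann-Whitney test at 0.05, 80% power. It states no allowance for removed records. Section 1.0 gives the project's goal as to "create decision support tools for Latina, Black, and non-Latina White women under age 50 with varying levels of health literacy". Appendix C says that the questionnaires are in a separate document, so the scoring of a blank cannot be seen.

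**The concern.** No answer to a question about overdetection or downsides has two possible meanings: the woman is not engaged, or she does not know. The first bears on data quality; the second is a knowledge result. The rule does not separate them and deletes the whole record, so decisional conflict and informed choice are lost as well.

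Read literally, it gives odd results:

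- Four blank items before exposure and four complete answers after: removed, although the post-exposure answers are complete.
- Four good answers before and three of four blank after: kept, with one usable post-exposure answer.
- Two blanks before and two after because she does not know: removed, not recorded as low knowledge.

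At stake are the comparability of the retained arms, since half the trigger items follow randomization and exposure, and the planning data for the larger trial. Women with low health literacy, whom the tool is meant to include, are plausibly among the likeliest to leave open items blank.

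**Working it through.** **1. The plan's own figure.** Inputs from section 6.0: difference 13, SD 20, one-sided alpha 0.05, power 80%. For two means, n = 2 × [20 × (1.645 + 0.842)/13]² = 29.3, so 30 per arm. Dividing by the Mann-Whitney efficiency 3/π (0.955) gives 30.7, so 31. The stated 33 is within 2 of this. Power at 33 per arm is 0.825 by the asymptotic formula and 0.820 by simulation.

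**2. Effect of removal on a mean.** If a fraction f of an arm is removed and those women have mean r, the retained mean is (m − f·r)/(1 − f). The values of f and r below are illustrative.

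- Equal removal of equally low scorers (f = 0.10, r = 40 in both arms): control (57 − 4)/0.90 = 58.9; tool (70 − 4)/0.90 = 73.3; difference 14.4.
- More removal in control (f = 0.15 against 0.05, r = 40 in both): control (57 − 6)/0.85 = 60.0; tool (70 − 2)/0.95 = 71.6; difference 11.6.

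The direction therefore depends on who is removed in each arm.

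**3. Simulation of the four-of-eight rule, logistic blank model.** Assumptions: true means 57 and 70, SD 20, pre/post correlation 0.6. The chance of a blank depends on the score to varying degrees. Disengaged women skip 60% of items and gain nothing from the tool; the overall difference is held at 13.

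| Who leaves items blank | Removed, control / tool | Retained means | Difference |
|---|---|---|---|
| Low-knowledge women, weakest case | 6.7% / 3.9% | 58.9 / 71.2 | 12.3 |
| Low-knowledge women, strongest case | 19.3% / 12.2% | 62.6 / 73.6 | 11.0 |
| Unrelated to knowledge | 4.2% / 4.1% | 57.0 / 70.0 | 13.0 |
| 10% disengaged, moderate knowledge link | 14.3% / 11.6% | 58.8 / 72.2 | 13.4 |
| 20% disengaged, weak knowledge link | 16.9% / 16.7% | 57.1 / 72.7 | 15.5 |

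**4. A second blank model.** Scores are clipped to 0-100, the correlation is 0.5, and each item is blank with probability (1 − score/100) × c. At a score of 57 and c = 0.50 that is 0.43 × 0.50 = 0.215 per item. Clipping puts the unscrubbed control mean at 56.9 and the difference at 12.5.

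- c = 0.25: about 1% removed, no material effect.
- c = 0.50: 10% of control and 7% of tool women removed; control mean 58.7; difference 12.0. Check by step 2, with removed control women averaging about 41: (56.9 − 0.10 × 41)/0.90 = 58.7.
- c = 0.75: 28% and 20% removed; control mean 62.1; difference 11.3.

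Adding 10% or 20% disengaged women who gain nothing, 70% of whom the rule catches, makes scrubbing raise the difference at c = 0.25 (11.3 to 12.1; 10.0 to 11.5) and at c = 0.50 (11.3 to 11.7; 10.0 to 11.2). At c = 0.75 the two mechanisms roughly offset each other.

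**5. Where the power goes.** Second model, no disengaged women, 33 per arm before removal:

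| | c = 0.50 | c = 0.75 |
|---|---|---|
| No scrubbing | 0.81 | 0.81 |
| Scrubbed | 0.79 | 0.68 |
| Same numbers removed at random | 0.79 | 0.70 |
| Scrubbed, but 33 retained per arm | 0.80 | 0.80 |

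Repeat runs differ by up to about 0.02. At c = 0.75 the loss is 0.81 − 0.68 = 0.13, of which random removal of equal numbers accounts for 0.81 − 0.70 = 0.11. Truncation costs about 0.01, because the SD shrinks along with the difference. The asymptotic formula agrees: with 10%, 20% and 30% of records lost and not replaced (29.7, 26.4 and 23.1 per arm), power is 0.79, 0.75 and 0.70.

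**The case against.** The rule is prespecified and tracked, and the study is a feasibility study recruiting from market-research panels, where disengaged respondents are plausible and a quality filter is reasonable. One blank does not trigger removal: the threshold is four of eight, and wrong but comprehensible English answers stay in. The overdetection items ask women to guess. The documents do not say whether a don't-know answer counts as non-response, whether these eight items feed the 0-100 score, how blanks are scored, or whether answers are forced. No blank rate is given, and at the lowest rate examined nothing material happens. Scoring every skipped item as not correct has its own cost, since it treats inattention as ignorance.

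All of this stands as a limit on the size and certainty of the effect. It does not remove the defect. The text makes non-response to knowledge items a ground for deletion, with no provision for a blank that means not knowing, and the guessing prompt covers only two of the eight items.

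A reader might infer that the rule necessarily shrinks the tool effect. The documents do not support that: it requires blanks to come from not knowing and to fall more heavily on control, and disengagement pushes the other way. A reader might also infer that truncating the score costs power. The split in step 5 shows that the loss is almost all lost sample size, which any removal rule causes if records are not replaced; the documents do not say whether they are.

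**Conclusion.** The point holds in a direction-neutral form. Section 5.2.4 lets blanks on knowledge questions, half of them asked after exposure, decide whether a randomized woman is analyzed. Where blanks reflect low knowledge, both arm means are too high: the control mean moves from about 57 to 59-62 when roughly 7-28% of control women are removed. Against a true difference of 13, the retained difference was 11.0-12.3 when blanks tracked knowledge, 13.0 when they were unrelated to it, and 13.4-15.5 when 10-20% of women were disengaged. These ranges rest on assumed blank rates, pre/post correlations of 0.5-0.6 and assumed disengagement. That blanks would otherwise be scored as wrong is a proposal, not something the documents state. The uncertain direction is itself a reason to change the rule before the data are scrubbed.

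**What to change.** In section 5.2.4:

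1. Delete non-response as a ground for removal.
2. In the main analysis, keep all eligible randomized women whose records are otherwise genuine. Score a blank or don't-know answer on a knowledge item as not correct, and state this in the scoring key.
3. Limit removal on open answers to evidence of a non-genuine record: nonsensical text or non-English answers on at least four of the eight items.
4. Report removals by arm and reason.
5. Show the data set scrubbed under the present rule as a sensitivity analysis.

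The cost is a wording change, a line in the scoring key and one extra analysis; reasons for removal are already tracked. The downside is that some inattentive panel members stay in with low scores, which may dilute the difference. The sensitivity analysis will show by how much the two data sets differ. Post-exposure answers can still lead to removal under item 3, but on authenticity and not on knowledge, and the counts by arm will show any imbalance.

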6.0 STATISTICAL CONSIDERATIONS

Stratification will be based on racial/ethnic groups (e.g., Latina, Black, non-Latina White). For adequate power, 66 participants from each racial/ethnic group will be enrolled and randomized (198 total).

For knowledge, previous research shows that mean knowledge score is 57 out of 100.³⁶ Compared to usual care, decision aids increased knowledge 13 points (mean difference 13.34 out of 100; 95% CI [11.17,15.51]).³⁶ For decisional conflict scale (0-100), those using a decision aid were more informed by 7 points (mean difference: -7.26 of 100; 95% CI [-9.73, -4.78]), and were more clear

about their personal values by 6 points (mean difference: -6.09; 95% CI [-8.50, -3.67]). ³⁶ Finally, fewer were passive in decision-making (risk ratio 0.66; 95% CI [0.53 to 0.81]). ³⁶ Using a one-sided Mann-Whitney Test, a sample size of 33 provides 80% power at the 0.05 significance level (alpha) to detect a mean knowledge difference of 13 with an estimated standard deviation (SD) of 20, and to detect a mean decision conflict score difference of 6.5 with an estimated SD of 10. Additionally, using a Mantel-Haenszel test, a sample size of 33 provides 80% power at the 0.05 significance level (alpha) to detect a risk ratio of 1.66 assuming the proportion of the informed values-based choice of 0.45 and 0.75 in the control and intervention groups, respectively. Subsequently, to detect the differences between groups with 80% power and 5% Type I error, 33 participants in each control and intervention group will yield a statistically significant preliminary effect. We are making multiple comparisons and recognize that the overall Type I error rate in this study will be greater than 5%. However, this study will allow us to collect adequate data, for planning future large scale studies.

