2.0 OBJECTIVES

To evaluate the potential for implementing the developed decision support tools with Latina, Black, and non-Latina White women in order to collect feasibility data, including acceptability, usability, and limited-efficacy, to prepare for a larger randomized controlled trial.

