5.0 STUDY PLAN

5.1 Study Design

To conduct a preliminary evaluation of the decision support tool, up to 36 women will be recruited to review the decision tool and complete questionnaires to assess informed choice, decisional conflict and confidence, and acceptability. To inform the feasibility testing, 36 women will be randomized to test randomization, measures, and recruitment.

Following this preliminary evaluation of the decision tool and feasibility testing, 198 participants will be randomized on a 1:1 basis to review the decision support tool or control condition of standard breast cancer screening education. Black, Latina, and Non-Latina White participants will be assigned to either the control or intervention condition using 4 and 2 varying block size. They will complete the pre-questionnaire, review the decision support tool/control condition, and complete the post-questionnaire.

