5.2.3 Participation

Measures will elicit participants' perceptions of the tool (Appendix A)/control condition (Appendix B). These measures assess acceptability and informed choice using knowledge, attitudes, intentions, priorities, and values.

Pre-tool/control condition questionnaires are:

- Sociodemographic characteristics (Appendix J)
- Knowledge of Screening Mammography Guidelines and Perceived Benefits and Harms of Screening Mammography (Appendix D)
- Decision Conflict Scale (which collects feelings of being fully informed and clear about the importance of the components for making informed decisions) (Appendix E)
- Decision Self-Efficacy (Appendix F)

Post-tool/control condition questionnaires are:

- Acceptability (Appendix G)
- Preparation for Decision Making Scale (Appendix H)
- Decision Conflict Scale
- Decision Self-Efficacy
- Knowledge of Screening Mammography Guidelines and Perceived Benefits and Harms of Screening Mammography
- Health literacy and health numeracy (Appendix I)

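### Knowledge, decisional conflict and self-efficacy are measured before and after the material, but Section 6.0 uses no pre-scores and plans no effect estimate with a confidence interval

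*Combined protocol and SAP*

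**What the plan says.** Section 5.1 sets the sequence for the 198 randomized women: "They will complete the pre-questionnaire, review the decision support tool/control condition, and complete the post-questionnaire". Section 5.2.3 puts three measures in both questionnaires: the Decision Conflict Scale, Decision Self-Efficacy and the knowledge measure, listed for the pre-questionnaire as "Knowledge of Screening Mammography Guidelines and Perceived Benefits and Harms of Screening Mammography (Appendix D").

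Section 6.0 is the only statistical section. Its method for scores appears inside the sample-size argument: "Using a one-sided Mann-Whitney Test, a sample size of 33 provides 80% power at the 0.05 significance level (alpha"). The target for knowledge is "to detect a mean knowledge difference of 13 with an estimated standard deviation (SD) of 20". The second score has a target of the same standardised size: "to detect a mean decision conflict score difference of 6.5 with an estimated SD of 10". A Mantel-Haenszel test is named for informed values-based choice. Decision self-efficacy is not mentioned. The confidence intervals in the section all belong to the cited earlier research; none is planned for this trial's own results.

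On purpose, Section 2.0 says the feasibility data are collected "to prepare for a larger randomized controlled trial", and Section 6.0 closes by saying that "this study will allow us to collect adequate data, for planning future large scale studies".

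**The concern.** The plan collects a baseline value of each repeated outcome from every randomized woman and then gives it no role in the analysis. The only stated use of pre-tool answers is the record-removal rule in Section 5.2.4, which is data cleaning.

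Three things follow.

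- **Precision.** Comparing randomized arms without the baseline is valid, but it is less precise when pre- and post-scores are correlated. The loss matters most within a racial/ethnic group, where there are 33 per arm and where the study was sized.
- **An open choice of outcome.** With both scores available, the Mann-Whitney test could be run on post scores or on changes. The two have different power, and the plan does not fix which is meant.
- **Planning value.** A larger trial needs an effect estimate with its uncertainty, an SD and a pre-post correlation. A one-sided rank-test p-value supplies none of these, and Section 6.0 specifies no other output.

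**Working it through.** **Inputs from Section 6.0.** Knowledge: difference 13, SD 20. Decisional conflict: difference 6.5, SD 10. Both give d = 13/20 = 6.5/10 = 0.65. One-sided alpha 0.05, 80% power, 33 per arm in each racial/ethnic group, and 3 × 33 = 99 per arm pooled.

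**Assumptions.** The documents do not give the pre-post correlation r, so r = 0, 0.3, 0.5 and 0.7 are tried. Scores are taken as normal with equal SDs before and after, 13 and 20 are read as post-score values, and all 33 per arm are analysed.

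**1. The plan's own figure.** For a comparison of two means, n = 2(1.645 + 0.842)²/0.65² = 29.3, so 30 per arm. Dividing by the Mann-Whitney efficiency 3/π = 0.955 gives 31.4, so 32, against the stated 33. Simulated Mann-Whitney power on post scores at 33 per arm is about 82%. The sample size reproduces, using one SD and no pre-post correlation.

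**2. Power by method within one group.** For ANCOVA, power is noncentral t with 63 df and noncentrality 0.65 × √(33/2) / √(1 − r²) = 2.640/√(1 − r²), which is 2.64, 2.77, 3.05 and 3.70. For change scores, the SD is 20 × √(2(1 − r)), which is 28.3, 23.7, 20.0 and 15.5. Change is therefore noisier than the post score when r is below 0.5. The Mann-Whitney and rank ANCOVA rows come from 40,000 simulated trials.

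| Method | r = 0 | 0.3 | 0.5 | 0.7 |
|---|---|---|---|---|
| Mann-Whitney, post score | 82% | 82% | 82% | 82% |
| Mann-Whitney, change | 56% | 70% | 82% | 95% |
| ANCOVA | 83% | 86% | 91% | 98% |
| Rank ANCOVA | 81% | 84% | 89% | 96% |

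Simulated ANCOVA power agrees with the formula: 82.8%, 85.8%, 91.1% and 97.6%. An unadjusted t-test has 83.3% power, so about 1.6 points of the ANCOVA advantage come from leaving the rank test. Like for like, rank ANCOVA against Mann-Whitney on post scores shows that adjustment alone adds about −1, 2, 7 and 15 points.

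**3. Precision for knowledge.** SE = 20 × √(2/n) × √(1 − r²), and the half-width is the 97.5% t quantile times the SE. The r = 0 column is the unadjusted comparison.

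| 95% half-width, points | r = 0 | 0.3 | 0.5 | 0.7 |
|---|---|---|---|---|
| 33 per arm | 9.8 | 9.4 | 8.5 | 7.0 |
| 99 per arm | 5.6 | 5.3 | 4.9 | 4.0 |

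For example, at 33 per arm and r = 0.5, the SE is 4.92 × 0.866 = 4.26, and 1.998 × 4.26 = 8.5. Half-widths for decisional conflict (SD 10) are half of these. Pooled power is already about 99.7% (Mann-Whitney) to 99.8% (t-test), so the pooled gain is in precision only.

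**The case against.** **The gain rests on an unknown r.** Nothing in the documents fixes r. Both arms read educational material between the two measurements, and at least one paired knowledge item in Section 5.2.4 is worded differently before and after, so a high r cannot be taken for granted. At r = 0.3, adjustment alone adds about 2 points of power, and the half-width moves only from 9.8 to 9.4. This stands, and it is why the benefit is given as a range.

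**The sizing points to post scores.** The 13 points are a difference against usual care, quoted beside a mean score, and the calculation uses one SD with no correlation. That is the more natural reading, but the plan does not say so, and one phrase would settle it. The change-score figures show what the open choice could cost; they are not evidence of lost power if post scores are tested.

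**Full retention is assumed.** Section 5.2.4 removes records after data collection, and the documents do not say whether they are replaced. With 30 or 26 analysed per arm (assumed retention), Mann-Whitney power on post scores would be about 78% or 73%. This limits the statement that 80% is met, but it does not weaken the case for adjustment.

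**The scales are bounded and the planners chose a rank test.** In a bounded, discrete 0–100 simulation, ANCOVA still had 82%, 85%, 90% and 97% power at the four correlations, against 81% for Mann-Whitney on post scores. It is true that rank ANCOVA is marginally below Mann-Whitney at r = 0 and does not itself give an adjusted mean difference.

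**This is a feasibility study that accepts an overall Type I error above 5%.** That makes estimation more important, because the planning quantities are its main product.

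**Conclusion.** The concern holds. Section 6.0 gives the pre-scores no role in the outcome analysis, leaves the tested score undefined, names no method for self-efficacy and plans no effect estimate with a confidence interval. The sample size is not wrong, and an unadjusted comparison would be valid.

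The cost in efficiency is small if r is about 0.3 and substantial if it is 0.5 to 0.7: ANCOVA raises power within a racial/ethnic group from about 82% to between 86% and 98%, and cuts the knowledge half-width by 0.4 to 2.8 points. Under the normal, equal-SD assumptions with 33 analysed per arm, ANCOVA had at least the power of either Mann-Whitney version at every r tried. The missing estimate, interval, SD and correlation are a gap whatever r turns out to be, given the study's stated purpose. The plan should be changed, because the improvement uses data already collected.

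**What to change.** Add to Section 6.0:

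- Post-material knowledge, decisional conflict and self-efficacy will each be analysed by ANCOVA with arm and the matching pre-material score, adding racial/ethnic stratum in the pooled analysis.
- The adjusted mean difference with its confidence interval, the residual SD and the pre-post correlation will be reported for each outcome.
- If residuals are badly skewed, rank ANCOVA will supply the test. Because it gives no adjusted mean difference, the ANCOVA estimate and interval should still be reported beside it.
- The Mann-Whitney test will be kept as a sensitivity analysis and stated to use post scores.

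The cost is a few sentences of SAP text and a few lines of analysis code. No new data or participants are needed.
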